#### 6.3.6. Dyschezia (pain associated with defecation)

Dyschezia will be assessed weekly via the eDiary and will be scored by the subject using a 0–10 NRS, where 0 represents no pain and 10 represents the worst pain imaginable.

#### 6.3.7. EHP-30, PGIC and question about severity of endometriosis condition

Subject will complete in addition two questionnaires in the eDiary: EHP-30 and PGIC (see APPENDIX C and APPENDIX D). EHP-30 will be completed at baseline and Weeks 12, 24 and 36 visits. PGIC will be completed at Weeks 12, 24 and 36 visits.

Subject will answer in the eDiary an additional question to describe the severity of her endometriosis condition over the preceding 4-week period, with following possible answers: no symptoms, very mild, mild, moderate, severe. This question will be asked every 28 days from day 1 up to week 36 included.

#### **6.3.8. Modified Biberoglu and Behrman questionnaire**

Endometriosis pain will be assessed by subject using the mB&B scale (see APPENDIX B) provided as paper questionnaire at screening visit and Weeks 12, 24 and 36 visits. This paper questionnaire will be kept as source data and corresponding scores recorded in eCRF by the Investigator.

On the same visits, a gynecological assessment including the assessment of the two clinical signs of the B&B - pelvic tenderness and pelvic induration (see APPENDIX B) - will be evaluated. Corresponding scores will be recorded in subject source data and in the eCRF by the Investigator.

### **6.4. SAFETY OBSERVATIONS AND MEASUREMENTS**

#### **6.4.1. Adverse Events**

AE data will be collected continuously during the study as described in Section 8.

AE data will be obtained at scheduled study visits based on physical examination, vital signs and biological laboratory assessments (see flowchart in APPENDIX A). In addition, subjects will report AEs spontaneously and/or through questioning.

Complete appropriate data on all AEs experienced for the duration of the reporting period, as defined in section 8, will be reported on an ongoing basis in the AE pages of the eCRF.

A complete physical examination, i.e. weight, examination of organ systems, including thyroid gland, lungs, heart, abdomen, liver, kidneys and peripheral pulses (by palpation, auscultation or percussion), eyes, ears, nose, throat and skin (by inspection) and neurological reflexes will be performed at Screening, on Day 1 and Weeks 12, 24 and 36 visits. In addition, a manual breast examination (by palpation) will be performed at Screening and Week 36. Results of the examinations will be recorded on source subject data file and in the eCRF. Medical conditions present at screening that do worsen in severity and/or frequency during the study will be reported as AEs in the corresponding eCRF page.

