### 3.2. SAFETY ENDPOINTS

- Change from baseline to weeks 12, 24 and 48 in BMD assessed by dual-energy X-ray absorptiometry (DXA) for femoral neck, hip and spine.
- Treatment emergent adverse events (TEAEs) frequency and severity.

- Changes in clinical laboratory assessments (haematology, coagulation parameters, biochemistry, hormones, lipids and urinalysis) from baseline to weeks 4, 8, 12, 16, 20, 24, 28 and 36.
- Any pathological changes from baseline in the endometrium as assessed by histology from endometrial biopsies performed at weeks 12 and 24 (and week 36 only if no endometrial biopsy was obtained at week 24 or diagnosis at week 24 was different from “benign endometrium”).

Change from baseline in any other safety parameter including weight, vital signs, gynecological assessment, breast assessment and endometrial thickness.

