### **6.2.1. Screening Period – Study Screening visit (11±5 weeks prior to Day 1 visit)**

The subject will be informed of the study objectives and overall requirements, and written informed consent will be obtained before performing any study-specific procedures that are not standard of care.

The subject will be considered as included into the study after the ICF is signed and dated by the subject and the Investigator or medical delegate.

The screening period will last up to 11±5 weeks during which the subject will be seen up to three times. During this time the following study screening assessments will be completed (see schedule of assessments in APPENDIX A):

- Demographic data, height and weight
- Medical history including concomitant diseases, obstetric/gynecological history and history of endometriosis including diagnosis and previous treatments
- Assessment of endometriosis pain with the mB&B scale (see APPENDIX B)
- Previous and current treatments recording
- Physical examination
- Vital signs (blood pressure and heart rate)
- Urine pregnancy test

- TVUS of uterus and ovaries to measure endometrium thickness, to rule out any clinically significant gynecological conditions which might interfere with the study efficacy and safety objectives and to confirm that the subject has no ovarian endometrioma  $\geq 7$  cm in diameter
- Gynecological examination, including the mB&B scale (see APPENDIX B) clinical signs reporting (pelvic tenderness and pelvic induration)
- Endometrium biopsy (should be performed at least 7 days after the first day of menstruation and sent for central assessment). If no tissue is available, the biopsy should be repeated as soon as possible in the following days.

The endometrium biopsy is not required at the screening visit for subjects having performed an endometrium biopsy within the past 6 months of the screening visit, which shows no endometrium atypical hyperplasia or adenocarcinoma and for which slides are available for current study assessment through retrospective central laboratory reading.

- PAP smear

A screening PAP smear is not required for subjects in whom a PAP smear was performed within the 12 months prior to the screening visit and which results indicate no clinically significant abnormalities requiring surgical intervention (e.g. LEEP or cervical conisation) and are available for source document verification.

- Manual breast examination (by palpation)

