##### **6.2.2.1. Baseline visit – Study visit Day 1**

If the subject has successfully completed all screening assessments and is between the first and seventh day (inclusive) of starting menstruation, she will go to the investigational site for the following evaluations and tests before drug administration:

- Confirm inclusion/exclusion criteria (randomization will not be postponed if the results of the endometrium biopsy done during the screening period are not available on Day 1)
- Previous and concomitant treatments recording
- AE recording
- Physical examination
- Vital signs (blood pressure and heart rate)
- Urinary protein dipstick
- eDiary check for good completion

- EHP-30 questionnaire (see APPENDIX C) completion by the subject
- Urine pregnancy test
- Contraception counselling

The subject will receive double barrier contraception (condoms with spermicide) if necessary. It will be provided upon need at each subsequent visit over the duration of the study.

In view of the invasive nature of the following assessments it is recommended to perform these upon confirmation from the eDiary data that the subject meets the study entry requirement and upon receipt of the screening central laboratory results and confirmation that the values meet the study entry requirement. The following procedures will be performed and recorded as part of the screening/baseline assessments, prior to the first administration of study treatment:

- Fasting blood samples for haematology, coagulation parameters, chemistry, lipids, hormones and OBE2109 and KP017 pre-dose plasma levels assessments.
- BMD assessed by DXA for femoral neck, hip and spine. DXA can be performed up to 10 days after baseline.

The DXA scans will be read centrally.

The subject will then be randomized to one of the six treatment groups and will be provided with the study drug and analgesics. The subject will be instructed on how to take the study medication, analgesics, and on how to record the administration in the eDiary. The analgesics provided will be used only as rescue medication; no prophylactic use of analgesics is allowed during the whole study. The subject will be provided as necessary with analgesics at each subsequent visit to cover study period until Week 36.

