## APPENDIX A SCHEDULE OF STUDY ASSESSMENTS

Timing 	Screening	Part A				Part B			Follow-Up		
	11±5 weeks	Day 1	W4	W8	W12	W16	W20	W24	W28	W36	W48
Informed Consent	X										
Demography, height, weight, medical history	X							X 		X 	
Previous/concomitant medication	X	X	X	X	X	X	X	X	X	X	X 
Inclusion-Exclusion criteria	X	X									
Physical examination	X	X			X			X		X	
Vital signs	X	X	X	X	X	X	X	X	X	X	
Gynecological examination and mB&B	X				X			X		X	
Breast manual examination	X									X	
Pap test	X										
Endometrium TVUS	X				X			X		X	
Endometrial biopsy	X				X 			X 		X 	
Clinical laboratory & urinary protein dipstick	X	X	X	X	X	X	X	X	X	X	
Blood sample for PK 		X 	X 	X	X	X 	X	X			
OBE2109/Placebo taken daily		←—————→									
Subject eDiary completion training/check 	X	X	X	X	X	X	X	X	X	X	
EHP-30		X			X			X		X	
PGIC					X			X		X	
BMD by DXA		X			X			X			X
Urine pregnancy test and contraceptive counselling	X	X	X	X	X	X	X	X	X	X	
Question regarding treatment received during study								X			
Adverse events	X	X	X	X	X	X	X	X	X	X	X 

 All post-baseline visits should take place at the end of the defined period (i.e. week 4 visit should be scheduled at the end of week 4, week 8 visit should be scheduled at the end of week 8, etc.). Post-baseline visits dates are calculated from Day 1 visit date.

 If endometrium thickness in TVUS is ≤ 5 mm, no endometrium biopsy will be necessary, as far as the screening biopsy has provided assessable results.

 If diagnosis at week 24 was different from “benign endometrium” or if no endometrial biopsy was obtained at week 24, then endometrial biopsy must be performed.

 PK blood samples should be taken after dosing except on Day 1 when taken before and 1.5 to 2 h after dosing, and at week 4 and 16, when taken prior to dosing.

 eDiary completion includes daily record of pelvic pain scores, uterine bleeding, dyspareunia symptoms, analgesic use, study treatment, difficulty in performing daily activities, weekly record of dyschezia pain score and 4-weekly record of patient’s impression of severity.

 Only weight will be recorded. Record in eCRF only if related to BMD (any medications with potential impact on BMD or any AEs related to BMD loss).

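### Section 6.4.1 puts weight in the Day 1 and Week 12 examinations, but Appendix A and the visit lists do not; if the schedule is followed, weight change has no scheduled placebo comparison

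*Combined protocol and SAP*

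**What the plan says.** Section 6.4.1 makes weight the first component of the physical examination ("A complete physical examination, i.e. weight, examination of organ systems"). The sentence ends by giving the visits: "neurological reflexes will be performed at Screening, on Day 1 and Weeks 12, 24 and 36 visits". The same paragraph says where the findings go: "Results of the examinations will be recorded on source subject data file and in the eCRF".

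Appendix A handles weight differently. It has a row for the physical examination, marked at Screening, Day 1 and Weeks 12, 24 and 36. Weight sits in another row, "Demography, height, weight, medical history", marked at Screening, Week 24 and Week 36 and blank at Day 1 and Week 12. The footnote to the Week 24 and Week 36 marks reads "Only weight will be recorded".

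The visit lists in section 6.2 follow Appendix A. Section 6.2.1 lists "Demographic data, height and weight" apart from the physical examination, and the Week 24 and Week 36 lists (6.2.3.2 and 6.2.4.2) also give weight its own line next to the examination. The Day 1 list (6.2.2.1) has "Physical examination" and no weight line, and the Week 12 list (6.2.2.3) is the same.

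Section 3.2 names the endpoint: "Change from baseline in any other safety parameter including weight, vital signs". It gives no time points for weight. Section 9.5.1 describes baseline data only as data collected before treatment, so a screening or a Day 1 weight would qualify.

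**The concern.** Three sets of instructions cover the same measurement, and they disagree at two visits. Day 1 is the natural baseline. Week 12 is the end of the only period with a placebo control. A site coordinator or eCRF designer normally works from the schedule and the visit lists. In both of those, weight is written out separately wherever it is wanted and left out at Day 1 and Week 12, so the plausible result is that it is not recorded at either visit.

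Section 9.5.4 intends safety to be assessed against baseline and across treatment groups. Section 9.6.1 provides for an analysis of Part A safety and efficacy data, which the sponsor will use to plan later studies. If the schedule prevails, that analysis would hold no scheduled post-baseline weight for any arm. A Week 12 weight that was not taken cannot be recovered later.

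**Working it through.** No power, error-rate or event calculation bears on this point. The check is to set the sources side by side and count the scheduled weights that fall in the placebo period.

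| Visit | Weight under 6.4.1 | Weight row, Appendix A | Weight line, 6.2 visit list | Placebo arm's status |
|---|---|---|---|---|
| Screening | yes | yes | yes (6.2.1) | untreated |
| Day 1 | yes | blank | none (6.2.2.1) | before first dose |
| Week 12 | yes | blank | none (6.2.2.3) | end of 12 weeks of placebo |
| Week 24 | yes | yes | yes (6.2.3.2) | after 12 weeks of 100 mg |
| Week 36 | yes | yes | yes (6.2.4.2) | off treatment, after 100 mg |

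1. **Disagreement.** The sources conflict at 2 of the 5 visits that 6.4.1 names: Day 1 and Week 12.

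2. **Placebo period.** Section 4 moves all placebo subjects to 100 mg daily after Part A. Under 6.2.2.3 the first Part B dose is taken the morning after the Week 12 visit, so a weight at that visit still belongs wholly to the placebo period. Scheduled post-baseline weights in that period are 1 under 6.4.1 (Week 12) and 0 under Appendix A and the visit lists.

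3. **Age of the baseline.** If there is no Day 1 weight, baseline falls back to the screening visit, which 6.2.1 places 11 ± 5 weeks before Day 1. That is 11 − 5 = 6 weeks to 11 + 5 = 16 weeks before first dose. The first scheduled change, at Week 24, would then span 24 + 6 = 30 to 24 + 16 = 40 weeks, of which 24 are on study treatment.

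4. **Which reading a site would adopt.** If the examination line already covered weight, the separate weight lines at Screening, Week 24 and Week 36 would be redundant, and so would the footnote in Appendix A. That favours the reading in which weight is not taken at Day 1 or Week 12. It does not settle the matter, because 6.4.1 is explicit.

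**The case against.** The best reply is that nothing is missing. Appendix A and the visit lists do call for a physical examination at Day 1 and Week 12, and 6.4.1 says what that examination contains and that its results go to the eCRF. On this reading the schedule supplies the headings and 6.4.1 the content, so both weights are already required. No section says that weight is omitted at those visits. This stands as a possible reading, and it makes the consequence conditional. It does not remove the conflict, because it leaves the separate weight lines and the footnote without a purpose.

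A reader might infer several stronger things that the documents do not support:

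- **That the plan definitely has no placebo-controlled weight change.** This follows only if the schedule prevails over 6.4.1.
- **That none of the roughly 55 placebo subjects would have a weight from the placebo period.** Section 6.7.2 sends anyone who discontinues between Day 1 and Week 24 through the Week 24 procedures, which include weight. A placebo subject leaving in Part A would therefore be weighed. Such subjects are a selected few and cannot stand in for a group comparison, but the count is not strictly zero.
- **That no drug effect on weight could be estimated.** Section 7.2 keeps the fixed 50, 75, 100 and 200 mg arms on the same dose through Week 24. Differences among them at Week 24 remain randomized comparisons. Only the contrast with placebo is at risk.
- **That the pharmacokinetic work needs a Day 1 weight.** Section 1.6 cites the expected average weight of the population to support the dose range, and 9.5.6 speaks of possible covariates without naming any. A screening weight is collected in either case. A Day 1 value would be a preference.

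It is also fair to say that the stakes are modest. Weight falls within a general category of other safety parameters, and section 9.5.4 rules out formal testing of safety data.

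**Conclusion.** The inconsistency is real: 6.4.1 on one side, Appendix A and the section 6.2 visit lists on the other, differing at Day 1 and Week 12. Its consequence is conditional. Assuming that sites and the eCRF follow the schedule, scheduled post-baseline weights under placebo fall from one to none, and baseline becomes a value about 6 to 16 weeks old at first dose. Change in weight could then be described within arms and compared among the fixed active doses at Week 24, but not compared with placebo as randomized groups.

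This is a minor point. It affects one descriptive safety endpoint and leaves the primary analysis and the sample size untouched. It is still more than a wording correction, because Week 12 is the only scheduled opportunity for a placebo-controlled reading of that endpoint. The documents do not show how sites in fact acted, nor how much weight might drift between screening and Day 1, so no size of bias can be given.

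**What to change.** Reconcile the sections in line with 6.4.1:

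- Mark weight in the Day 1 and Week 12 columns of Appendix A, with the weight-only footnote extended to both, and add a weight line to lists 6.2.2.1 and 6.2.2.3.
- Make sure the eCRF has a weight field at both visits.
- Define baseline weight as the Day 1 value, and state the time points for change in weight, which section 3.2 leaves open.
- Report change to Week 12 by arm in the Part A safety analysis, with the two 75 mg arms pooled as section 9.5 already provides.

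The cost is two marks in the schedule, two lines of text and two eCRF fields. Both visits already include a physical examination, so the change adds no visit and no invasive procedure.

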#### **6.4.2. Vital signs**

Blood pressure (BP) and heart rate will be measured in sitting position at each monthly visit from the screening visit to the Week 36 visit. In case of abnormal vital signs (i.e. BP  $\geq$  150/100 mmHg or  $\leq$  90/50 mmHg and/or heart rate  $\geq$  100 bpm or  $\leq$  40 bpm) and if abnormality was not pre-existing, a repeat assessment after 5 min should be taken. In case of confirmed abnormality, an AE must systematically be reported by the Investigator in the eCRF AE page. The Investigator is to provide a diagnosis rather than reporting of individual vital signs parameters whenever possible.

#### **6.4.3. Transvaginal ultrasound and endometrial biopsies**

Endometrial thickness, uterus volume and abnormality (fibroids, adenomyosis, etc...) and left/right ovary abnormality status will be assessed by TVUS during screening, at weeks 12, 24 and 36. The print-

outs of the ultrasound will be interpreted and commented by the gynaecologist and kept as source data. Results of the examination will be recorded on source data forms and in the eCRF.

Endometrial biopsies will be performed for histological assessment during screening, at weeks 12 and 24. At week 36, endometrial biopsy will only be taken if no endometrial biopsy was obtained at week 24 or diagnosis at week 24 was different from “benign endometrium”. Endometrial biopsy samples will be performed with the Pipelle de Cornier® (APPENDIX E), as it will be described in the manual provided by the central laboratory. Endometrial biopsies will be centrally assessed by one single independent pathologist blinded to treatment group.

If at week 12 and week 24, the endometrium thickness in TVUS is  $\leq 5$  mm, no endometrium biopsy will be necessary, as far as the screening biopsy has provided assessable results. In this case the biopsy should be taken at week 36. However, if the week 24 biopsy result is available and indicated a benign endometrium then another biopsy is not required at week 36. Appropriate photo documentation of the endometrium thickness is mandatory and should be kept in the source documents at site.

#### **6.4.4. Bone mineral density and DXA**

Bone mineral density (BMD) of femoral neck, hip and spine will be assessed by DXA at baseline, weeks 12, 24 and 48. Instructions to measure the BMD and specific subject withdrawal criteria based on BMD will be provided in a specific imaging manual, which will be provided to the Investigator. The DXA scans will be transferred to a central reading unit who will assess the BMD blinded to treatment group.

#### **6.4.5. Laboratory parameters**

Haematology, coagulation parameters, chemistry, lipids and hormones (serum levels of E2, progesterone [P4] and LH) will be assessed from blood samples taken at screening, Day 1 and weeks 4, 8, 12, 16, 20, 24, 28 and 36. Serum levels of the anti-müllerian hormone (AMH) will be assessed on Day 1 and serum levels of the sex hormone-binding globulin (SHBG) will be assessed on Day 1 and weeks 12 and 24. Blood samples will be analyzed by the central laboratory. Details of blood sampling process, sample handling and shipment are described separately in a laboratory manual provided by the central laboratory. Central laboratory reference ranges will be filed in the investigator site file and in the trial master file. All laboratory results except E2, AMH, SHBG, P4 and LH levels will be assessed by the Investigator/sub-investigator and clinically significant abnormalities compared to screening/baseline status will be reported as AEs in the eCRF. E2, AMH, SHBG, P4 and LH levels will not be communicated to keep the operational team and the sites blinded to treatment administration.

The laboratory parameters are listed in APPENDIX F.

#### **6.5. OBE2109 AND KP017 PLASMA LEVELS**

PK blood samples will be collected from each subject for determining OBE2109 and KP017 plasma levels.

On Day 1, blood samples for PK assessment will be taken pre-first dose and 1.5 to 2 h post-first dose.

On the day of the site visits of weeks 8, 12, 20 and 24, the subject will take her daily dose of IMP at home at the usual time in the morning. The blood samples for PK will be taken at the site. The time of

dose administration in the morning and time of PK sampling on the same day will be recorded on the eCRF.

On weeks 4 and 16 visits, the subject will be asked to take the dose of IMP at site, after a pre-dose PK sampling. The time of dose administration on the previous day and time of taking of the PK sample will be recorded on the eCRF.

Details of blood sampling process, sample handling and shipment are described separately in a laboratory manual provided by the central laboratory.

## 6.6. CONCOMITANT MEDICATIONS AND THERAPIES

The Investigator will record in the appropriate section of the eCRF all concomitant medications taken by the subject during the study, from the date of signature of informed consent and for the duration of the reporting period as defined in section 8.5. From week 36 onwards, only concomitant medication with potential impact on BMD will be recorded in the eCRF.

The use of provided analgesics for endometriosis related pain will be recorded solely in the eDiary.

